**Methodology:**

We propose a multi-center, two cohort Phase II clinical trial to investigate the effectiveness of adding daratumumab to ibrutinib in WM patients. Cohort A will consist of patients who are ibrutinib naïve and appropriate for ibrutinib based treatment. Cohort B will consist of patients who have achieved a response plateau less than a complete remission (CR) on single agent ibrutinib.

Subjects in Cohort A will be identified by their treating physician and eligible for enrollment if they are treatment naïve or ibrutinib naïve after prior therapy and eligible for ibrutinib based treatment. Subjects in Cohort B will be identified by their treating physician and eligible for enrollment if they have had at least 6 months of exposure to single agent ibrutinib and demonstrate an IgM response plateau defined by two IgM measurements, at least 8 weeks apart that have changed <15% from the previous mark. In Cohort B response assessment will be measured from initial IgM level prior to ibrutinib initiation. Enrolled subjects will be prescribed commercial ibrutinib, 420mg PO daily. The investigational agent, daratumumab will be administered based on FDA approved dosing in multiple myeloma (16mg/kg) with 8 weekly induction treatments during Cycles 1 and 2, followed by every other week dosing for Cycles 3-6, then monthly dosing from Cycle 7 until Cycle 24 at which point they will continue with ibrutinib as monotherapy until Cycle 52 (4 years total) which is the predefined study completion for enrolled subjects at which point they will complete follow-up.

Study visits and response assessments with IgM measurements will occur with each cycle for the first year then every three cycles after cycle 13. Subjects with measurable extramedullary disease will have CT scans every 6 cycles until radiographic CR. Patients will be considered evaluable for response if they completed the initial 8 weeks of daratumumab induction therapy and evaluable for toxicity if receiving one dose of daratumumab. Patients will continue on combination therapy for 2 years or until disease progression or unacceptable toxicities at which point patients will come off trial. Patients achieving a CR after two years of combination therapy will be given an option to continue with single agent commercial ibrutinib.

Subjects to be enrolled	24 total subjects, 12 in Cohort A and 12 in Cohort B
Study Duration	6 years
Accrual period	2 years

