#### **Treatment Phases:**

Treatment will consist of induction, continuation, and maintenance phases. Induction will be defined as the first 2 cycles of combination treatment. The consolidation phase will include treatment with daratumumab on day 1 and day 15 of each cycle starting with cycle 3 through cycle 6. Starting at cycle 7 subjects will enter the maintenance phase with monthly daratumumab infusions until Cycle 24 day 1 (two years) at which point they will complete their combination treatment with daratumumab. Cycle 25 and beyond patients will continue on ibrutinib monotherapy.

Subjects will have doctor visits on each day of treatment with daratumumab but required study visits will only occur monthly for the first year followed by every 3 cycles for the remainder of the study. On non-study visits during induction, subjects will have baseline labwork considered to be standard of care obtained at the discretion of the investigator followed by daratumumab infusions. Subjects will take three, 140mg capsules of ibrutinib orally, daily starting on the same day as infusion and continue daily through all cycles.

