Study visits and response assessments with IgM measurements will occur day 1 of each cycle through cycle 13 then day of 1 every three cycles after the first year on treatment. Subjects with measurable extramedullary disease will have CT scans every 6 months while on study or until radiographic CR at which point they will occur at the discretion of the investigator. Patients will be considered evaluable for response if they completed the initial 8 weeks of daratumumab induction therapy. Response assessment in Cohort B will be measured from the IgM level recorded prior to ibrutinib initiation. Subjects will continue on combination therapy for 2 years until disease progression or unacceptable toxicities at which point patients will stop daratumumab therapy and come off study. All subjects will be followed for 1 year after completing combination therapy unless they come off study early for other reasons. Subjects achieving a CR will be given an option to continue with single agent commercial ibrutinib or stop all therapy.

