#### **7.2. Inclusion Criteria**

- 1)** Subjects must have a diagnosis of WM and meet the requirements for active therapy as defined by the 2nd International Workshop on Waldenstrom's Macroglobulinemia (see **Appendix A** for indications for therapy).
- 2)** Age  $\geq 18$  years of age
- 3)** Ibrutinib naïve or previously treated patients currently on ibrutinib with a plateau in disease response are eligible to participate.
  - a)** Ibrutinib naïve subjects may be either treatment naïve or previously treated but ibrutinib naïve to enter cohort A.
  - b)** Subjects entering cohort B must have a plateau response on ibrutinib defined as  $\geq 6$  months of ibrutinib treatment with 2 IgM measurements at least 2 months apart with  $\leq 15\%$  change from the previous measurement. Subjects with IgM level  $< 0.7$  g/dL will be eligible if their IgM level increases  $< 0.15$  g/dL over two IgM measurements as defined above.
- 4)** Subjects must have measurable disease defined by a serum IgM level  $\geq 0.5$  g/dL
- 5)** Eastern Cooperative Oncology Group performance status of 0-2
- 6)** Hematology values must be within the following limits:

- a. Absolute neutrophil count (ANC)  $\geq 1000/\text{mm}^3$  independent of growth factor support for 7 days of study entry if cytopenias are due to marrow involvement.
- b. Platelets  $\geq 50,000/\text{mm}^3$  independent of transfusion support within 7 days of study entry. TPO mimetics are not allowed to meet eligibility criteria.
- c. Hemoglobin  $\geq 8\text{g/dL}$ , independent of transfusion support within 7 days of study entry

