### **7.3. Exclusion Criteria**

- 1) Subject does not have a recorded IgM level recorded within 3 months prior to ibrutinib initiation.**
- 2) Subject meeting definition of disease progression while on ibrutinib. Subjects with IgM levels  $< 0.7\text{g/dL}$  are given special consideration. Please see inclusion criteria for 2b.**
- 3) Subjects in cohort B experiencing ongoing non hematologic toxicities attributable to ibrutinib  $>$  Grade 1 will be excluded from study entry.**
- 4) Major surgery or a wound that has not fully healed within 4 weeks of enrollment.**
- 5) Evidence of disease transformation at time of enrollment.**
- 6) Waldenstrom's complicated by amyloidosis**
- 7) Known central nervous system lymphoma.**

- 8) History of stroke or intracranial hemorrhage within 6 months prior to randomization.
- 9) Requires anticoagulation with warfarin or equivalent vitamin K antagonists (eg, phenprocoumon).
- 10) Requires chronic treatment with strong CYP3A inhibitors. Subjects that required strong CYP3A inhibitors but completed a course of treatment can be considered for enrollment after a washout period of 14 days prior to study drug administration.
- 11) Requires strong CYP3A inducers. Subjects that required strong CYP3A inducers but completed a course of treatment can be considered for enrollment after a washout period of 14 days prior to study drug administration.
- 12) Patients with history of Chronic Obstructive Pulmonary Disease or Reactive Airway disease must have PFTs with FEV1 calculated. Patients with a  $FEV1 \leq 50\%$  of predicted normal will be excluded.
- 13) Clinically significant cardiovascular disease such as uncontrolled or symptomatic arrhythmias, congestive heart failure, or myocardial infarction within 6 months of Screening, or any Class 3 (moderate) or Class 4 (severe) cardiac disease as defined by the New York Heart Association Functional Classification.
- 14) Vaccinated with live, attenuated vaccines within 4 weeks of randomization.
- 15) Seropositive for human immunodeficiency virus (HIV)

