### **Induction Phase**

The induction phase will consist of two cycles of continuous ibrutinib daily dosing in combination with eight weekly doses of daratumumab. Daratumumab dosing can occur within a window of  $\pm 3$  days. Induction will be defined as the first 8 weeks of combination treatment.

Subjects in Cohort A will begin the induction phase after the one cycle ibrutinib lead-in. Subjects in Cohort B will begin overall study treatment with Cycle 1 of the induction phase.

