### **10. Treatment Administration**

Treatment will be administered on an outpatient basis. Appropriate dose modifications for daratumumab and ibrutinib are described in Section 6.

Ibrutinib will be administered as 3, 140mg capsules daily for a total daily dose of 420mg. Subjects will be asked to take the capsules orally with or without food. Subjects will take the pills on a continuous daily basis with once cycle of treatment consisting of 28 days. Subjects will take their first dose of ibrutinib before or after their daratumumab infusion. On days in which they do not receive a daratumumab infusion, they will be asked to take their ibrutinib capsules at the same time each day. Subjects will continue daily dosing of ibrutinib until disease progression, toxicities, or study completion whichever comes first.

Daratumumab will be administered per the current package insert. Subjects will receive 16mg/kg weekly for 8 total doses. They will then receive 16mg/kg of daratumumab every other week starting on Cycle 3-6. From Cycle 7-24, subjects will receive daratumumab 16mg/kg on an every 4 week basis until disease progression, toxicities or study completion whichever comes first. Subjects will be premedicated with 100mg of methylprednisolone intravenously (IV), 650mg of

acetaminophen PO, and 25-50mg of Benadryl IV all taking 30 minutes prior to infusions with daratumumab. Methylprednisolone dosing may be reduced to 60mg IV with subsequent doses after the first infusion if no adverse events are recorded. Subjects will be asked to take 20mg of methylprednisolone PO for two days after each infusion and this can be eliminated after completion of the first cycle at the investigators discretion if no adverse events are recorded.

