### **12.3. Ibrutinib Administration**

Ibrutinib 420 mg (1m 420mg tablet) is administered orally once daily. The tablet is to be taken around the same time each day with 8 ounces (approximately 240 mL) of water. The tablet

should be swallowed intact and subjects should not attempt to open capsules or dissolve them in water. During treatment days with daratumumab combination dosing, ibrutinib should be taken 0-2 hours prior to daratumumab with 8 ounces of water.

If a dose is not taken at the scheduled time, it can be taken as soon as possible on the same day with a return to the normal schedule the following day. The subject should not take extra capsules to make up the missed dose. The first dose will be delivered in the clinic on Day 1, after which subsequent dosing is typically on an outpatient basis. Ibrutinib will be dispensed to subjects in bottles at each visit. Unused ibrutinib dispensed during previous visits must be returned to the site and drug accountability records updated at each visit. Returned capsules must not be dispensed to anyone.

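### Cohort B's plateau criterion fixes no ibrutinib dose, so a patient stable on a reduced dose could go up to 420 mg as daratumumab starts, and a resulting IgM fall could count as deepening

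*Combined protocol and SAP*

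**What the plan says.** **Entry.** Section 7.2, criterion 3b, and synopsis criterion 2b open identically: "Subjects entering cohort B must have a plateau response on ibrutinib defined as" 6 months or more on ibrutinib plus two IgM values at least 2 months apart, within 15% of each other. There is a special allowance for IgM below 0.7 g/dL. The Methodology synopsis and Section 1 add that the prior ibrutinib was single-agent. None of these texts gives a dose or asks that the dose be stable.

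**On-study dose.** The synopsis (Methodology) says "Enrolled subjects will be prescribed commercial ibrutinib, 420mg PO daily". Section 10 says "Ibrutinib will be administered as 3, 140mg capsules daily for a total daily dose of 420mg", and Section 12.3 says "Ibrutinib 420 mg (1m 420mg tablet) is administered orally once daily". The synopsis (Treatment Phases) says "Subjects will take three, 140mg capsules of ibrutinib orally, daily starting on the same day as infusion and continue daily through all cycles". None of these makes an exception for a subject already on a lower dose because of toxicity.

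**Sequence.** Section 9.3 gives the one-cycle ibrutinib lead-in to Cohort A only. For the other cohort, "Subjects in Cohort B will begin overall study treatment with Cycle 1 of the induction phase".

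**Endpoint.** Section 1.2 lists deepening of response in Cohort B once daratumumab is added, as a secondary objective. Section 1 states "Response assessment in Cohort B will be measured from the IgM level recorded prior to ibrutinib initiation". Section 16 reports the percentage of patients who deepen, descriptively. Section 14.1 defines the response categories but not deepening, and gives no rule for a change in ibrutinib dose.

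**The concern.** Cohort B has no control group. Its reading depends on one thing changing at Cycle 1 Day 1: daratumumab is added to an ibrutinib effect that has levelled off. If ibrutinib dose rises on the same day, two things change at once. Because response is referenced to the IgM level before any ibrutinib, the response category reflects the total fall and cannot show which drug produced the latest part of it.

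The 15% stability test does not help. It can screen out a recent dose change that moved IgM, but a patient who has been steady on a lower dose passes it.

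**Working it through.** The plan gives no figure on this point. Its one design calculation is the exact 95% interval in Section 16 for a 15% toxicity proportion with 12 patients. It reproduces (0.15 × 12 = 1.8 events; 1.57% to 46.54%, width 44.97%) and is not in dispute.

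**Step 1: can a reduced-dose patient get in, and would anything hold the dose down?**

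| Provision | What it covers | Does it prevent the rise? |
|---|---|---|
| 7.2, criterion 3b | Duration and IgM stability | No; dose not mentioned |
| 7.3, exclusion 3: "Subjects in cohort B experiencing ongoing non hematologic toxicities attributable to ibrutinib" above Grade 1 | Ongoing non-hematologic toxicity | No, if toxicity resolved on the lower dose or was hematologic |
| 7.3, exclusion 18 | Investigator judgement on conditions endangering the subject or the study outcomes | Discretionary only |
| 10.2, Table 2 | Reductions for CYP3A inhibitors (140 or 70 mg) | Only for those patients, while the inhibitor continues |
| 12.4.2 | 280 mg, then 140 mg, for repeated toxicities listed in 12.4 | No; it is written for events on study |
| 13.2 | Ibrutinib used per its FDA labeling | Unclear; does not say whether an earlier reduction stands against the 420 mg instruction |

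The eligibility text admits the patient, and no provision clearly stops the increase.

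**Step 2: could the increase matter for IgM?** The plan treats IgM as sensitive to ibrutinib exposure. Section 3 describes a rapid rise when dosing is interrupted, and Section 14.1 discounts rises attributed to holds longer than 7 days. That is evidence for drug versus no drug. The documents give no clinical comparison of lower doses with 420 mg. If pre-entry reductions used the 12.4.2 levels (an assumption), the dose ratio would be 420/280 = 1.5 or 420/140 = 3.0. These are dose ratios, not IgM effects.

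**Step 3: how large a fall would change a category?** The further fall needed from the plateau value is 1 − (1 − target reduction)/(1 − current reduction).

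- Plateau at 45% reduction, to reach PR (50%): 1 − 0.50/0.55 = 9.1%.
- Plateau at 40%, to PR: 1 − 0.50/0.60 = 16.7%.
- Plateau at 85%, to the 90% threshold for VGPR: 1 − 0.10/0.15 = 33.3%.

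The plateau positions are illustrative. Near a boundary a small fall is enough; further away it is not.

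**Step 4: effect on the reported proportion.** One misclassified patient moves it by 1/n. Section 14.2 requires completion of Cycle 2 for response evaluation, so n may be below 12: 1/12 = 8.3 points, 1/11 = 9.1, 1/10 = 10.0.

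**Step 5: how likely is at least one such entrant?** The documents give no frequency. With an assumed share p of eligible patients on a reduced dose, the chance of at least one among 12 is 1 − (1 − p)^12: 46% for p = 5%, 72% for 10%, 93% for 20%. If p is zero, so is the chance.

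**The case against.** The strongest reply is that no sentence tells a site to raise a Cohort B patient's dose. The synopsis line about starting ibrutinib on the infusion day cannot be literal for either cohort, because Cohort A starts a cycle earlier and Cohort B is already taking it. Ibrutinib is commercial supply used per label, and a sensible site might keep the lower dose. This stands in part: a reader might infer that the plan orders re-escalation, and it does not do so expressly. But the 420 mg instruction appears in several places without exception, so following the text raises the dose, and sites that depart from it would treat similar patients differently.

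A second reply is that the size is unknown at both steps. This stands fully. A reader might take 8.3 to 10.0 points as the bias in the deepening rate. It is only the weight of one patient, whatever the reason for misclassification.

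Third, the trial is a descriptive pilot with a safety primary endpoint, and concurrent medications are recorded at screening, so the entry dose should be retrievable and could be listed. That limits the consequence. Listing would identify the affected patients but could not separate the two drugs' effects.

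Fourth, a reader might infer that returning intolerant patients to full dose is a separate safety defect. The documents do not carry that far: Section 12.4.2 accepts restarting at the original dose after a first qualifying toxicity, and exclusions 3 and 18 give partial protection.

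**Conclusion.** The gap is real and more than a missing detail: for an eligible patient on a stable reduced dose, the plan as written raises ibrutinib and starts daratumumab together, and any resulting IgM fall can enter the deepening proportion. The size cannot be estimated. The number of such patients may be zero, the IgM effect of moving from a lower dose to 420 mg is not given, and what can be computed is 8.3 points per misclassified patient at 12 evaluable. The conclusion assumes that sites apply the 420 mg text as it stands.

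The documents do not support saying that Cohort B's result is biased. They support saying that it could be, through a route that is easily closed. The endpoint is secondary and descriptive, so no formal test is affected. This is a cheap improvement.

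**What to change.** Add to Section 7.2, criterion 3b, and to synopsis criterion 2b:

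> Both qualifying IgM measurements are taken on the same stable ibrutinib dose of 420 mg daily, continued unchanged to Cycle 1 Day 1, with no ibrutinib hold or CYP3A-related dose change between the first qualifying IgM measurement and Cycle 1 Day 1.

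The clause should not ask a toxicity-reduced candidate to return to 420 mg in order to qualify, since that would move re-exposure of intolerant patients outside study monitoring. Nor should it exempt procedural holds or Table 2 reductions. IgM recovering after a hold, or ibrutinib returning to full dose when an inhibitor stops, would leave the same overlap with daratumumab. The screening marrow need not cause a hold, because Section 10.2.2 allows bone marrow biopsy on ibrutinib.

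If the sponsor prefers to keep reduced-dose patients, there is an alternative in three parts:

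- require the same dose at both qualifying IgM values;
- state in Sections 10 and 12.3, with matching synopsis text, that this entry dose is continued unchanged and not raised to 420 mg;
- report deepening with each patient's entry dose listed.

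**Cost.** The preferred version is one clause in two places. A few candidates would be excluded, or delayed by about 2 months while they re-qualify, and the disease is rare. The alternative avoids excluding patients for a stable reduced dose, but needs edits to the dosing text and accepts mixed background doses in a cohort of 12.

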**7) Biochemical values within the following limits:**

- d. Alanine aminotransferase (ALT) and aspartate aminotransferase (AST)  $\leq 3 \times$  upper limit of normal (ULN)
- e. Total bilirubin  $\leq 2 \times$  ULN unless bilirubin rise is due to Gilbert's syndrome or of non-hepatic origin
- f. Creatinine clearance (CLcr)  $> 25 \text{ ml/min}$

**8) Women of childbearing potential and men who are sexually active must be practicing a highly effective method of birth control during and after the study consistent with local regulations regarding the use of birth control methods for subjects participating in clinical trials. Men must agree to not donate sperm during and after the study. For females, these restrictions apply for 1 month after the last dose of study drug. For males, these restrictions apply for 3 months after the last dose of study drug.**

**9) Women of childbearing potential must have a negative serum (beta-human chorionic gonadotropin [ $\beta$ -hCG]) or urine pregnancy test at Screening. Women who are pregnant or breastfeeding are ineligible for this study.**

Subjects must sign (or their legally-acceptable representatives must sign) an informed consent indicating that they understand the rational of the study and can participate in all study procedures.

### **7.3. Exclusion Criteria**

- 1) Subject does not have a recorded IgM level recorded within 3 months prior to ibrutinib initiation.**
- 2) Subject meeting definition of disease progression while on ibrutinib. Subjects with IgM levels  $< 0.7\text{g/dL}$  are given special consideration. Please see inclusion criteria for 2b.**
- 3) Subjects in cohort B experiencing ongoing non hematologic toxicities attributable to ibrutinib  $>$  Grade 1 will be excluded from study entry.**
- 4) Major surgery or a wound that has not fully healed within 4 weeks of enrollment.**
- 5) Evidence of disease transformation at time of enrollment.**
- 6) Waldenstrom's complicated by amyloidosis**
- 7) Known central nervous system lymphoma.**

- 8) History of stroke or intracranial hemorrhage within 6 months prior to randomization.
- 9) Requires anticoagulation with warfarin or equivalent vitamin K antagonists (eg, phenprocoumon).
- 10) Requires chronic treatment with strong CYP3A inhibitors. Subjects that required strong CYP3A inhibitors but completed a course of treatment can be considered for enrollment after a washout period of 14 days prior to study drug administration.
- 11) Requires strong CYP3A inducers. Subjects that required strong CYP3A inducers but completed a course of treatment can be considered for enrollment after a washout period of 14 days prior to study drug administration.
- 12) Patients with history of Chronic Obstructive Pulmonary Disease or Reactive Airway disease must have PFTs with FEV1 calculated. Patients with a  $FEV1 \leq 50\%$  of predicted normal will be excluded.
- 13) Clinically significant cardiovascular disease such as uncontrolled or symptomatic arrhythmias, congestive heart failure, or myocardial infarction within 6 months of Screening, or any Class 3 (moderate) or Class 4 (severe) cardiac disease as defined by the New York Heart Association Functional Classification.
- 14) Vaccinated with live, attenuated vaccines within 4 weeks of randomization.
- 15) Seropositive for human immunodeficiency virus (HIV)
- 16) Seropositive for hepatitis B (defined by a positive test for hepatitis B surface antigen [HBsAg]). Subjects with resolved infection (i.e., subjects who are HBsAg negative but positive for antibodies to hepatitis B core antigen [anti-HBc] and/or antibodies to hepatitis B surface antigen [anti-HBs]) must be screened using real-time polymerase chain reaction (PCR) measurement of hepatitis B virus (HBV) DNA levels. Those who are PCR positive will be excluded. EXCEPTION: Subjects with serologic findings suggestive of HBV vaccination (anti-HBs positivity as the only serologic marker) AND a known history of prior HBV vaccination, do not need to be tested for HBV DNA by PCR.
- 17) Seropositive for hepatitis C (except in the setting of a sustained virologic response [SVR], defined as aviremia at least 12 weeks after completion of antiviral therapy).
- 18) Any life-threatening illness, medical condition, or organ system dysfunction which, in the investigator's opinion, could compromise the subject's safety, interfere with the absorption or metabolism of ibrutinib capsules, or put the study outcomes at undue risk.
- 19) Active malignancy not treated with curative intent within 2 years of study entry. Nonmelanomatous skin cancers and cervical carcinoma in situ are excluded.

